4.6.3.3 Expectedness

Expected adverse reactions are collected in a standardized format. The expectedness is assessed based on previously observed adverse events. If the nature, severity, or frequency of an AE does not match the risk information described in previous studies of the intervention, it shall be considered unexpected.

4.6.4 Timing of adverse event assessment

Assessments shall be conducted after the patient signs the informed consent form and within 4 weeks after the end of the trial. Follow-up shall be performed according to the severity of the AE to observe its outcome.

4.6.5 Reporting of adverse events

Once an AE occurs, details including the time of occurrence, management process, duration, and outcome shall be recorded in the case report form (CRF). For adverse events of moderate severity or above, the principal investigator, department head, and ethics committee shall be notified within 24 hours.

For SAE, regardless of the cause, the investigator shall provide appropriate and timely medical treatment for the subject. This responsibility shall be explicitly stated in the study protocol and reaffirmed during investigator training. A SAE Report Form shall be completed and promptly submitted to the regulatory authorities, while simultaneously informing all participating sites and notifying the study sponsor.

4.7 Date management

An electronic data capture system will be used in this study for data entry management. When the data entry is complete, the database will perform consistency check automatically. On trial-specific documents, except for the signed consent, the participant will be referred to by a unique trial-specific code in any database, not by name. All data sets will be password protected. Modifications to data stored in the electronic database will be documented via a data change system. All paper

documents are to be stored in numerical order and maintained safely in confidential conditions for a period of 3 years after completion of the study. The project investigator will have access to all data sets.

4.8 Sample size calculation

Sample size was estimated using SAS version 9.4, with ADAS-cog12 at week 14 as the designated primary outcome measure. Based on the results of previous studies(10), we assume a treatment difference of approximately 3.0 with a standard deviation of 6.0. Considering a 10% non-adherence to treatment and a 10% loss to follow-up, 80 randomized patients per arm or 160 randomized patients in total (128 completers), will have more than 80% power and a type I error rate of 5% for the ADAS-cog12 comparison to detect a significant treatment difference.

4.9 Statistical analysis

All analyses were pre-specified in a statistical analysis plan finalized before database lock. The primary analysis followed a modified intention-to-treat (mITT) principle, including all randomized participants with at least one post-baseline efficacy assessment. A per-protocol (PP) analysis was performed as a sensitivity analysis, excluding participants with major protocol deviations (<85% intervention adherence or violation of inclusion criteria). Changes from baseline in ADAS-cog12 scores were analyzed using linear mixed-effects models (LMMs) with repeated measures. The models included fixed effects for treatment group (active vs. sham), time, and their interaction, as well as sex, AD drug use history and TCM pattern; age, years of education, time since diagnosis, and baseline ADAS-cog12 score were included as covariates. A random intercept for each participant was used, with an unstructured covariance matrix. MMSE, ADCS-ADL23, and NPI outcomes were analyzed using the same model structure. Pre-specified subgroup analyses were conducted by TCM pattern, age, sex, and education levels. Continuous outcomes were summarized as means with 95% confidence intervals (CIs). The LMM framework accommodated missing data under the missing-at-random assumption. In addition, multiple imputation using fully conditional specification was conducted for primary and key secondary endpoints as sensitivity analyses. All statistical tests were two-sided with a significance threshold of 0.05. Analyses were performed using SAS software, version 9.4 (SAS Institute, Cary, NC, USA).

16S rRNA gene sequencing analysis are performed using QIIME and R packages (v3.2.0). OTU-level alpha diversity indices are calculated using the OTU table in QIIME. OTU-level ranked abundance curves are calculated to assess OTUs richness and evenness among samples. Beta diversity analysis will be performed to investigate the structural variation of microbial communities across samples using UniFrac distance metrics and visualized via PCoA. The linear discriminant analysis (LDA) effect size method is used to characterize the taxa with statistical significance and biological relevance. The set value of the LDA score is 2. Partial least-squares-latent structure discriminate analysis is performed using Simca-P 14.0 (Umetrics AB, Sweden) to observe the fecal microbiota pattern in different groups based on OTUs of the sequencing data from each sample. Variables with variable importance in projection >1 are identified as important contributors to generation of the model. The functional profile of KEGG

Orthology for each sample will be predicted from 16S rRNA amplicon data with Phylogenetic Investigation of Communities by Reconstruction of Unobserved States. To test the overall correlation between changes in microbiome and altered outcome variables, pairwise Spearman's rank correlations within the active and sham acupuncture groups at baseline, 14 and 28 weeks are calculated and adjustments are performed using the Benjamini–Hochberg procedure and Spearman rho values are filtered with a false discovery rate at 5%.

5 Trial monitoring

An independent DSMB is established to review accumulating study data on a periodic basis and make recommendations to protect the safety of the participants. The members of the DSMB include a recognized expert in the field of AD, a senior acupuncturist, and a statistician. All members are external to our institute. Only the DSMB is authorized to evaluate unblinded interim efficacy and safety analyses. An interim analysis is proposed to be conducted after approximately 50% of participants had completed the week 14 assessments. According to the Haybittle–Peto stopping guideline, the trial would be considered for early termination only if the interim analysis demonstrated overwhelming evidence of efficacy ($P < 0.001$) or raised serious safety concerns based on recommendations from the independent Data and Safety Monitoring Board (DSMB). Otherwise, the study would continue as planned until the final analysis.

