16S rRNA gene sequencing analysis will be performed. Bacterial diversity will be determined by α -diversity (Chao1 richness estimator, Abundance-based Coverage Estimator metric, Shannon diversity index, and Simpson index) and β -diversity (Principle coordinates analysis, PCoA). To further reveal the linking hypotheses of “acupuncture-gut microbiota-AD” axis, the functional profile of Kyoto Encyclopedia of Genes and Genomes (KEGG) Orthology for each sample will be predicted. The participants and their caregivers will be instructed under tutoring video to collect a fresh fecal sample using sample collection kits, packaged within insulated containers and chilled with frozen gel packs. All fecal samples will be dispensed in 2 ml Eppendorf tubes and immediately stored in -80°C until analysis. Total bacterial genomic DNA samples are extracted using the Fast DNA SPIN extraction kits (MP Biomedicals, Santa Ana, CA, USA), following the manufacturer’s instruction. DNA quantity is determined using the Nanodrop1000 spectrophotometer (Thermo Fisher Scientific, Waltham, MA, USA), and quality is assessed by 1.0% agarose gel electrophoresis. PCR amplification of the bacterial 16S rRNA gene V3–V4 region is performed in a multiplex approach. The amplicons will be purified using Agencourt AMPure XP Beads (Beckman Coulter, Indianapolis, IN, USA) and quantified using the PicoGreen dsDNA Assay Kit (Invitrogen, Carlsbad, CA, USA). Then the final equimolar pool will be sequenced using an Illumina MiSeq platform according to the manufacturer’s recommendations. The Quantitative Insights into Microbial Ecology (QIIME, v1.8.0) pipeline is employed to process the sequencing data. Operational taxonomic units (OTUs) are defined by clustering sequences using the UCLUST algorithm and a similarity threshold of 97% against the Greengenes database.

The treatment credibility scale will be assessed at the end of session 1 and session 42 by asking participants to rate their response to four questions on a 5-point scale developed by Borkovec and Nau [32]. The first assessment allows us to test the participants’ blinding before sustained efficacy is evident. The second assessment will allow us to detect the association of efficacy with beliefs about treatment received.

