4.1 Confidence intervals and P values

All statistical tests were two-sided with a significance threshold of 0.05. Adjustments for multiple comparisons were not applied for secondary endpoints. Continuous outcomes were summarized as means with 95% confidence intervals (CIs).

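### The LDA effect size step calls taxa statistically significant on an LDA cut-off of 2 alone, without the false-discovery control used for the correlations in the same section

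*Protocol*

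**What the plan says.** The 16S rRNA part of Protocol 4.9 lists several analyses. For individual taxa it says: "The linear discriminant analysis (LDA) effect size method is used to characterize the taxa with statistical significance and biological relevance". The next sentence gives the only decision rule: "The set value of the LDA score is 2". This step has no alpha of its own, no adjusted p-value, no named contrast and no named visit.

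False-discovery control appears later in the same section, in the sentence on correlations between microbiome and outcome variables: "adjustments are performed using the Benjamini–Hochberg procedure and Spearman rho values are filtered with a false discovery rate at 5" per cent.

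The only general threshold is in the preceding part of Protocol 4.9: "All statistical tests were two-sided with a significance threshold of 0.05". The SAP schedules fecal samples (3.7) but describes no microbiome analysis. Its one multiplicity statement is in 4.1: "Adjustments for multiple comparisons were not applied for secondary endpoints".

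The number of taxa to be tested is not given. Protocol 4.5 says only how OTUs are formed, by clustering at 97% similarity. The microbiome question is the third objective in Protocol section 2, and samples are due at weeks 0, 14 and 28.

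**The concern.** Testing many taxa one by one at 0.05 produces positives by chance in proportion to the number tested. An LDA cut-off screens on the size of a difference, not on its reproducibility, so a chance difference in an abundant taxon can pass it. The authors recognised multiplicity in this section, because they control it for the correlations, but they wrote no control for the taxon screen.

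What is at stake is the wording of the result. Taxa that pass the screen are to be described as having statistical significance, and a reader would take such a list as evidence on the third objective. Under the written rule, such a list can appear when no taxon differs at all.

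**Working it through.** **Inputs from the documents.** General alpha 0.05, two-sided (Protocol 4.9); LDA cut-off 2 (Protocol 4.9); 128 completers, 1:1, so 64 per arm (Protocol 4.8 and 4.3).

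**Inputs assumed.** Taxa tested, m: 20 to 400. The 0.05 level applies to this step. The comparison is active against sham at one visit.

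**The plan's own figure.** Only the sample size can be reproduced, and here it serves only to fix n. With a difference of 3.0 and SD 6.0, the normal approximation gives 63 per arm. The t-test needs 64 (power 0.801; 63 gives 0.795). Then 64/(1 − 0.20) = 80 per arm, or 160 in total, as stated.

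**Step 1: before any LDA filter, no true differences, independent tests.** Expected false positives = 0.05 × m; P(at least one) = 1 − 0.95^m.

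| m | Expected false | P(≥1) | P(≥3) |
|---|---|---|---|
| 20 | 1.0 | 0.64 | 0.08 |
| 50 | 2.5 | 0.92 | 0.46 |
| 100 | 5.0 | 0.99 | 0.88 |
| 200 | 10.0 | >0.999 | 0.998 |

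Correlation between taxa changes the spread of these counts, not their mean.

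**Step 2: adding the cut-off, by simulation under no difference.** 64 per arm, log-normal abundances (log-scale SD 2.0 between taxa, 1.5 within), 20,000 reads per sample, taxa present in at least 10% of samples, rank test at p<0.05, 200 data sets per m. The LDA score was approximated as log10(1 + half the absolute mean difference per million) and required to be at least 2. The LDA effect size software itself was not run.

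| m | Mean with p<0.05 | Mean also passing LDA ≥2 | P(≥1) | P(≥3) | P(any taxon) with Benjamini–Hochberg 5% |
|---|---|---|---|---|---|
| 20 | 0.97 | 0.9 | 0.57 | 0.09 | 0.04 |
| 50 | 2.23 | 1.9 | 0.85 | 0.26 | 0.045 |
| 100 | 4.75 | 3.6 | 0.975 | 0.66 | 0.045 |
| 200 | 9.35 | 6.1 | 0.995 | 0.92 | 0.015 |
| 400 | 19.44 | 9.7 | 1.00 | 0.995 | 0.06 |

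In this model the cut-off removes 1 − 0.915/0.97 = 6% of the false positives at m = 20 and 1 − 9.665/19.44 = 50% at m = 400. It thins the list but does not control the error.

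**Step 3: stability.** Further null runs with the same n and the same approximate score gave 1.2 false taxa at m = 20, about 2 at m = 50, 3.6 to 3.8 at m = 100, and 7 to 8 at m = 300. Across all runs, the chance of naming any taxon with Benjamini–Hochberg was roughly 1% to 9%. When nothing differs, any taxon named is false, so the nominal value is 5%; the scatter comes from the small numbers of data sets.

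**Step 4: visits.** These counts are for one comparison at one visit. Running the screen at both week 14 and week 28 would roughly double the expected number.

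**The case against.** The strongest reply is that the third objective asks whether a long-term effect is related to microbiota changes, and the analysis that tests this is the correlation step, which is already controlled at 5%. The LDA step stands beside ordination and functional prediction as description. The objective is itself conditional on a long-term effect, no taxon is a primary or secondary outcome, and the SAP leaves even secondary endpoints unadjusted. All of this stands, and it is why the point is minor. It does not remove the point, because the protocol does not call the step exploratory and describes its output with the words "is used to characterize the taxa with statistical significance and biological relevance".

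Three stronger readings are tempting, and the documents do not support them.

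- **That several taxa will be declared acupuncture-related when none are.** The number of taxa is not stated. At 20 to 50 taxa the expected count is one or two, and three or more becomes likely only from about 100. The contrast is not stated either, so linking the taxa to acupuncture is an inference.
- **That a score of 2 is too small to be biologically relevant.** The documents do not define the scale of the score, so they cannot settle this.
- **That the list drives the conclusion on the third objective.** Nothing says that taxa passing the screen are carried into the correlations or into any claim.

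It can also be said that the 0.05 sentence closes the clinical paragraph, which names SAS, while the 16S work uses QIIME and R. The sentence does say all tests, and no other level is given, but its use here remains an assumption.

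**Conclusion.** The concern holds as a minor one. The plan attaches statistical significance to taxa through an unadjusted screen, while the same section already contains the control that would make the label defensible. With no true difference, and the tests at 0.05, the expected false taxa per comparison after an approximate LDA filter are about 1 at 20 taxa, 2 at 50, 3 to 4 at 100, and 8 to 10 at 300 to 400. The chance of at least one is about 57% to 100%, against roughly 1% to 9% with Benjamini–Hochberg.

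These figures rest on an assumed number of taxa, an assumed abundance model, an approximate score and an assumed between-arm contrast. That the cut-off is not an error control does not depend on them. The FDR-controlled correlations, the ADAS-cog12 analysis and the sample size are unaffected.

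**What to change.** In the 16S part of Protocol 4.9:

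- State the contrast and time points for the LDA effect size step, for example active versus sham at weeks 14 and 28, and the rule for which taxa enter the tests.
- Apply Benjamini–Hochberg at 5% across all taxa tested at each time point, and call a taxon significant only if it passes.
- Report the LDA score as a descriptive effect size.
- Label taxa that pass only the unadjusted test and the cut-off of 2 as exploratory.

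The cost is one or two sentences and a few lines of R. The downside is a shorter list of taxa. No sample, visit or clinical analysis changes.

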- 1) To evaluate if adding acupuncture to donepezil improves outcomes in patients with mild AD;
- 2) If there is an effect of acupuncture, whether the previous effect of acupuncture treatment is present after washout;
- 3) If acupuncture has a long-term effect on AD, is it related to changes in gut microbiota?

3 Study design

This is a prospective, randomized, participant-masked, sham-controlled trial, with each eligible participant randomly assigned to either active or sham acupuncture added to donepezil treatment. All participants or their legal representatives will provide written informed consent and be treated in accordance with the tenets of the Declaration of Helsinki (version 2013).

Table 1 Trial summary

Title	An efficacy and safety trial of acupuncture as adjunct to donepezil in patients with mild AD
Clinical indication	Treatment of mild AD
Trial type	Interventional
Type of control	Sham/Placebo
Route of intervention	needle stimulation + oral
Trial blinding	Single-blind
Treatment groups	Active acupuncture for 14 weeks
	Sham acupuncture for 14 weeks
Concomitant therapy	Donepezil 5 mg QD for 28 weeks
Number of trial subjects	160 in total
Estimated duration of trial	The sponsor estimates that the trial will require approximately 2.5 years from the time the first participant signs the informed consent until the last participant's last visit.
Duration of participation	Each participant will participate in the trial for approximately 30 weeks from the time the participant signs the Informed Consent Form through the final contact. After a screening phase, each subject will receive assigned treatment for 28 weeks. After the end of treatment each participant will be followed for at least 14 days.
Randomization ratio	1:1

4 Methodology

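### The PLS-DA plot and VIP>1 taxon list planned for the stool data have no stated validation, so they cannot tell an acupuncture effect from noise

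*Protocol*

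**What the plan says.** Protocol section 2 lists a microbiota question as its third objective: "If acupuncture has a long-term effect on AD, is it related to changes in gut microbiota". Protocol 4.9 then sets out several analyses of the 16S data.

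- **PLS-DA.** "Partial least-squares-latent structure discriminate analysis is performed using Simca-P 14.0 (Umetrics AB, Sweden) to observe the fecal microbiota pattern in different groups". The groups and the visit are not defined, although stool is collected at weeks 0, 14 and 28.
- **Naming rule.** "Variables with variable importance in projection >1 are identified as important contributors to generation of the model".
- **LDA effect size screen.** "The set value of the LDA score is 2". No false discovery control is stated for it.
- **UniFrac distances.** These are displayed by PCoA, with no between-arm test stated.
- **Spearman correlations with outcome.** Here "adjustments are performed using the Benjamini–Hochberg procedure and Spearman rho values are filtered with a false discovery rate at 5" per cent.

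Neither document mentions cross-validation, Q2, a permutation test, a hold-out set or a rule for the number of PLS components. The SAP has no microbiome analysis; stool sampling appears only in its visit schedule (SAP 3.7).

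**The concern.** PLS-DA is supervised: it looks for the combination of OTUs that best separates the known labels. When OTUs are numerous relative to participants, it can find a separating combination in pure noise. The fitted plot therefore needs an out-of-sample or permutation check before it says anything about treatment.

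The VIP cut-off adds to the problem. VIP is scaled relative to the other variables in the same model, so a cut-off of 1 carries no error rate, and some taxa will pass it whether or not the arms differ. At stake is whether a published plot of two separated arms, with a list of named taxa, would be taken as evidence that acupuncture changes the gut microbiota.

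**Working it through.** **Sample size used.** The plan gives no size, power or error rate for the microbiota. Its only figure is for ADAS-cog12 (Protocol 4.8): "80 randomized patients per arm or 160 randomized patients in total (128 completers". That figure reproduces. With a difference of 3.0 and SD 6.0, n = 2 × (1.96 + 0.842)² × (6/3)² = 62.8, so 63 per arm. At 64 per arm the noncentral-t power is 80.1%, and 64/0.8 = 80 per arm. The check uses 64 per arm (128/2), repeated at 80.

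**Assumed inputs.** OTUs are defined at a "similarity threshold of 97% against the Greengenes database" (Protocol 4.5), but neither their number nor a filter is given, so 20 to 3000 features were tried. The number of components is also unstated; 1 to 3 were tried.

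**Algebra of VIP.** For feature j among p features, VIP_j² = p × Σ_a(S_a × w_ja²) / Σ_a S_a. Here S_a is the variation in arm explained by component a, and each weight vector has Σ_j w_ja² = 1. Summing over j gives Σ_j VIP_j² = p, so the mean squared VIP is 1 for any data. At least one feature must therefore exceed 1 unless all are equal. The algebra alone guarantees no more than that.

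The share above 1 under no effect can be approximated. With one component and independent features, the weights behave like normal noise. VIP>1 is then roughly |Z|>1, which has probability 2 × (1 − 0.8413) = 0.317.

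**Simulation with no arm difference.** Labels were assigned at random to sparse, correlated, OTU-like relative abundances with unit-variance scaling. Entries are means at 64 per arm; a dash means not run.

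| Features | Components | In-sample AUC | In-sample accuracy | 7-fold CV accuracy | Q2 | Share with VIP>1 |
|---|---|---|---|---|---|---|
| 20 | 1–2 | 0.68–0.70 | 62–64% | – | – | 36–38% |
| 50 | 1–2 | 0.78–0.83 | 70–74% | – | – | 36–39% |
| 100 | 1–2 | 0.84–0.92 | 75–83% | – | – | 36–40% |
| 200 | 2–3 | 0.97–0.99 | 91–95% | 49–50% | −0.28 to −0.42 | 39–40% |
| 500 | 1 | 0.94 | 86% | – | – | 36% |
| 500 | 2–3 | 0.997–1.000 | 97–99% | 49–50% | −0.22 to −0.25 | 39–40% |
| 1000 | 1 | 0.96 | 89% | – | – | 36% |
| 1000 | 2–3 | 1.000 | 99.2–99.5% | 48–50% | −0.18 to −0.19 | 39% |
| 3000 | 2–3 | 1.000 | 99.8–100% | 49% | −0.10 to −0.13 | 39% |

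Features that never varied were dropped. Of 483 kept at the 500 setting, about 190 were flagged; of about 920 kept at the 1000 setting, about 360. Even at 20 features, no data set had fewer than 4 flagged.

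**Sensitivity.**
- At 80 per arm with OTU-like data (200 to 3000 features, 2 to 3 components), in-sample accuracy was 88% to 100% and cross-validated accuracy 49% to 50%.
- With independent normal features, 32% to 36% had VIP>1 over the same range. At 20 and 50 features, in-sample accuracy was 65–66% and 74–77%.
- A further run with 1 to 2 components and 200 to 1000 features gave 93% to 100% in sample, about 50% cross-validated and negative Q2.

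**Does validation repair it?** In 300 no-effect data sets (300 OTUs, 2 components), a label-permutation test on 7-fold Q2 (99 permutations, P≤0.05) accepted the model in 4.7%. Q2 exceeded 0 in 1.0%. In-sample AUC exceeded 0.9 in all 300.

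**The case against.** The strongest reply is that this is description. The protocol introduces PLS-DA as a way to look at a pattern, and VIP>1 marks what drives the fitted model, not what acupuncture changed. Statistical significance is assigned to the LDA screen, and microbiota is not among the SAP's objectives or outcomes. All of this is fair and limits the weight of the point. It does not remove it: a fixed cut-off that names taxa is a selection rule, and a display that looks much the same with and without an effect does not inform the reader. The documents name only the software, so any validation it may run by default cannot be credited.

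Four stronger inferences are tempting, and the documents do not support them.

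- *That the microbiota objective would get an empty positive answer.* That objective asks whether a long-term effect is related to microbiota change. Protocol 4.9 assigns that link to the Spearman correlations, which have false discovery control.
- *That the arms separate whatever the data.* Separation depends on the OTU count and the number of components, neither of which is stated.
- *That a mean squared VIP of 1 forces a large share above 1.* It forces only one. The 32% to 40% is a no-effect result. With real signal in 1 to 20 independent normal features, the share was 10% to 28% at 500 features and 7% to 20% at 100. A long list is therefore no sign of an effect.
- *That the LDA screen's false-positive yield is known.* An uncorrected rank test at 0.05 flagged 4% to 5% of taxa under no effect, but that is just the nominal level. It omits the LDA cut-off and does not measure the planned screen.

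**Conclusion.** The point holds within limits. As written, the PLS-DA plot and VIP>1 list cannot distinguish an acupuncture effect from noise. With no arm difference, the rule names about 32% to 40% of features at every feature count tried. In-sample separation is near-complete from about 200 features with two or three components, is 86% to 89% accurate with one component at 500 to 1000 features, and is modest (about 62% to 77%) at 20 to 50. Where cross-validation was run, accuracy stayed near 50% with negative Q2.

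The result rests on an assumed OTU count, an assumed number of components, simulated abundances, and reading the undefined groups as active versus sham, which is natural but not explicit. It affects one exploratory method supporting the microbiota objective. The Spearman analysis and the ADAS-cog12 result are unaffected.

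**What to change.** In Protocol 4.9, and in a microbiome section added to the SAP:

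1. State the PLS-DA contrast (active versus sham), the visit, and the rule for choosing the number of components.
2. Beside every PLS-DA plot, report 7-fold cross-validated Q2 and a test that permutes arm labels between participants at least 1000 times.
3. Interpret VIP>1 taxa as differing between arms only if the permutation P<0.05; otherwise label them descriptive.
4. Base any claim of an overall arm difference on a permutation test of the UniFrac distances already computed.
5. Apply Benjamini-Hochberg at 5% to any per-taxon tests used to claim arm differences, including those behind the LDA screen. A significant model does not establish that each listed taxon differs.

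If stool results already exist, run these checks before reporting and say that they were added. The cost is a few lines of text and a little computing on the same data. The downside is that fewer taxa will be claimed.

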4.1 Participant recruitment

The study will take place in the Outpatient Department, Shanghai Research Institute of Acupuncture and Meridian, Shanghai, China. The recruitment will be announced via our official account on social media and forwarded once a month. Placement of brochures and study posters in Yueyang Hospital of Integrated Traditional Chinese and Western Medicine, Shanghai University of Traditional Chinese Medicine and Ruijin Hospital, Shanghai Jiaotong University School of Medicine (collaborating hospitals) and community centers will be used to assist recruitment. In addition, we conducted disease-related science lectures in the elderly community and put up posters in the community to further promote the recruitment. Participants or their representatives will be instructed to read the informed consent and those who showed interest in the study will be scheduled for the screening visit. After presenting written informed consent, participants will be examined, and if all entry criteria are met, will commence a 4-week run-in period of treatment with donepezil hydrochloride (5 mg/capsule, China) 5 mg daily (prior AD treatments will be terminated by then). To further avoid potential confounding effects on the clinical outcomes and gut microbiota, participants will be instructed to maintain their regular diet and activity level, and refrain from probiotics, prebiotics, or synbiotics use. Upon successful completion of the 4-week run-in, participants will be scheduled to complete baseline assessments and undergo randomization. The study flowchart and proposed trial schedule are shown in Figure 1 and Table 1, respectively.

[figure not shown]

Figure 1 Flow diagram of the study protocol

Table 2 Study schedule

Visit No.	V1	V2	V3	V4	V5	V6
End of Week Relative to Study Treatment Start	-4	0	7	14	21	28
Tolerance Interval for Visit (d)	0	0	±3	±3	±7	±7
Entry and Administrative						
Eligibility	X	X				
Informed consent	X					
Physical/neurological examination	X					X
Demographics	X					
Medical history	X					
Randomization		X				
Interventions						
Active/Sham acupuncture						
Donepezil						
Outcomes Measures						
ADAS-cog12		X	X	X	X	X
MMSE		X	X	X	X	X
ADCS-ADL		X	X	X	X	X
NPI		X	X	X	X	X
Fecal samples collection		X		X		X
Additional Assessment						
Adverse events						
Treatment compliance						

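### The microbiome–outcome analysis is meant to relate changes, but its stated computation is within-arm correlations at visits including baseline, with no change score defined, so as written it does not directly address Objective 3

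*Protocol*

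**What the plan says.** Objective 3 (Protocol 2, Objectives) is conditional and concerns change: "If acupuncture has a long-term effect on AD, is it related to changes in gut microbiota".

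The 16S rRNA part of Protocol 4.9 gives the matching purpose, "To test the overall correlation between changes in microbiome and altered outcome variables". The operation in the same sentence is pairwise Spearman "rank correlations within the active and sham acupuncture groups at baseline, 14 and 28 weeks are calculated", with Benjamini–Hochberg control at 5%. It defines no change from baseline, does not name the microbial and outcome variables to be paired, and states no comparison of the correlations between arms.

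The other microbiome analyses in that section are alpha diversity, UniFrac distances displayed by principal coordinates, LDA effect size with a threshold of 2, a predicted KEGG profile, and a partial least-squares discriminant analysis used "to observe the fecal microbiota pattern in different groups based on OTUs of the sequencing data from each sample". None of them uses a clinical outcome.

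Stool is scheduled at weeks 0, 14 and 28 in the Protocol 4.1 study schedule ("Fecal samples collection X X X"). The SAP repeats that schedule in 3.7, but its analysis section (6.1 to 6.4) contains no microbiome analysis.

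**The concern.** The stated aim and the stated computation concern different quantities. A correlation between levels at one visit reflects stable differences between people, such as diet, age or disease severity, as well as anything that happened during the trial. It can be present when change in microbiota and change in cognition are unrelated, and close to zero when they are clearly related.

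At stake is the interpretation of a numbered objective. Significant taxa could be reported as evidence that an acupuncture effect runs with microbiota change when they reflect only differences present before randomisation, and a real link between changes could be missed. Because each arm is analysed alone, a result that is significant in the active arm and not in the sham arm could be misread as specific to acupuncture.

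**Working it through.** **1. Reading the text.** For any variable Y, change from baseline at visit t is Y(t) − Y(0). At t = 0 it is zero for everyone, so no correlation of changes exists there. The baseline correlation must therefore use levels. The sentence gives one rule for all three visits and no switch of variable, so levels are the natural reading at weeks 14 and 28, though the text does not say so outright.

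**2. Per-arm number.** The documents give no sample size or target correlation for the microbiome analysis. The trial's own figure supplies the number per arm. Protocol 4.8: "we assume a treatment difference of approximately 3.0 with a standard deviation of 6.0". The normal approximation gives n = 2 × (1.96 + 0.84)² × (6/3)² ≈ 62.8, so 63 per arm. The t-test needs 64 (power 79.5% at 63, 80.1% at 64). Then 2 × 64 = 128 completers, and 128/(1 − 0.20) = 160 randomised. The trial size reproduces and is not in question; 64 per arm is used below.

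**3. Level against change correlation (illustration; every input except n is an assumption).** Within one arm, let the baseline levels of a microbial measure and an outcome have SD 1 and correlation r_b. Let their changes have SD s and correlation r_c, independent of baseline. Then

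follow-up level correlation = (r_b + s² r_c)/(1 + s²).

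- Case A: levels related, changes not (r_b = 0.4, r_c = 0).
- Case B: changes related, baseline levels not (r_b = 0, r_c = 0.4).

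Spearman tests were simulated with n = 64 and two-sided unadjusted p < 0.05 (4,000 runs at s = 0.6, 2,000 at the others).

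| Change SD s | A: level correlation | A: level test significant | B: level correlation | B: level test significant | B: change test significant |
|---|---|---|---|---|---|
| 0.3 | 0.4/1.09 = 0.37 | 82% | 0.036/1.09 = 0.03 | 6% | 89% |
| 0.6 | 0.4/1.36 = 0.29 | 60% | 0.144/1.36 = 0.11 | 12% | 89% |
| 1.0 | 0.4/2 = 0.20 | 32% | 0.4/2 = 0.20 | 35% | 87% |

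The correlations shown are the underlying linear values; the simulated Spearman values are slightly smaller. In case A the change test is significant in about 5% of runs, its nominal rate. At s = 1.0 the two cases have the same level correlation, so 32% and 35% differ only by simulation error, and the level test cannot tell the cases apart.

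**4. Within-arm testing.** If both arms share a true correlation of 0.3 (assumed) with 64 each, exactly one arm is significant in about 47% of simulated runs. A contrast in significance between arms is therefore not evidence of a difference in correlation.

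**The case against.** The strongest reply is that the sentence opens by naming changes, and that Protocol 4.5 and SAP 6.1 define the efficacy outcomes as changes in score. Change scores at weeks 14 and 28, with baseline levels for reference, are a possible reading. That stands to this extent: a reader might conclude that the plan definitely computes levels at all three visits, and the documents establish this only for baseline. It does not rescue the analysis. The switch of variable between visits is unstated, and the choice between levels and changes could be made after the data are seen.

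A reader might also infer that the trial cannot answer Objective 3. The documents do not support that. Stool and clinical scores are both scheduled at weeks 0, 14 and 28, so change can be computed; the shortfall is in the written analysis, not the data.

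Nor is it right that group differences in microbiota are ignored. LDA effect size assesses taxa for statistical significance and the discriminant analysis compares groups. A post-baseline comparison of randomised arms is valid even on levels. However, the LDA classes and time points are not given, change is not modelled, and neither analysis is linked to outcome.

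Two further points stand. The percentages depend on assumed variances and correlations. And the matter is mechanistic: microbiome measures are not among the listed primary or secondary outcomes, so no efficacy or safety conclusion rests on this sentence.

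**Conclusion.** The mismatch is real and worth correcting. The baseline correlation cannot test change, no change variable is defined for weeks 14 and 28, and nothing else in Protocol 4.9 or the SAP relates microbiota change to outcome. The sentence as written therefore does not directly address Objective 3.

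The documents fix no size for the problem. In the illustration, a level correlation flags an association with no link between changes in roughly 32% to 82% of runs, and detects a true change correlation of 0.4 in only 6% to 35%, where the change test detects 87% to 89%. These figures assume change independent of baseline, one measure in one arm, 64 participants and no false-discovery adjustment. The exact values move with the assumptions; that levels and changes can disagree in both directions does not depend on any one of the scenarios shown.

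**What to change.** In Protocol 4.9 and in a new microbiome section of the SAP:

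- Define change from baseline to week 14 and to week 28 for named diversity measures or taxa, and for ADAS-cog12 and the other clinical outcomes.
- Replace the visit-specific correlations with Spearman correlations between those changes, adjusted for the baseline values of both variables.
- Report them by arm with a formal test of the arm difference. Keep Benjamini–Hochberg at 5% and state which tests form the family.
- Keep the baseline correlation as descriptive only.
- Add a baseline-adjusted comparison of microbiota between arms at weeks 14 and 28.
- Label the change–change result exploratory. It is observational, remains open to confounding such as concurrent diet change, and is not randomised evidence of mediation.

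The cost is analysis wording; no visit or sample is added. There are two downsides. Participants without a paired stool sample drop out of this analysis. The test of the arm difference will also be weak: with 64 per arm, 80% power needs a difference in Fisher z of (1.96 + 0.84) × √(2 × 1.06/61) ≈ 0.52, for example a correlation of 0 in one arm and about 0.48 in the other. That limit should be stated with the result.
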